5.7.2 Handling of Participant Withdrawals or Termination

Subjects, who choose to withdraw consent, can do so by notifying the treating physician, the Principal Investigator or research staff in writing or verbally. Any data remaining after formal withdrawal, will be destroyed/discarded per Institutional guidelines. Subject will be informed whether the data will be retained and analyzed up to the point of withdrawal. The study team will document the reason for discontinuation in the subjects' research record. Every effort will be made to undertake protocol-specified safety follow-up procedures to capture AEs, serious adverse events (SAEs), and unanticipated problems (UPs). If subjects withdraw or discontinue early replacement participants will be allowed.

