5.7 Participant Withdrawal or Termination

5.7.1 Reasons for Withdrawal or Termination

Participants are free to withdraw from participation in the study at any time upon request for any reason, and without repercussion. Participants who withdraw consent will be counseled that their withdrawal only affects uses and sharing of information after their written request to withdraw authorization has been received, and that their authorization may not be withdrawn for uses or disclosures that have previously made or need to be made to complete analyses or report data from the research. For the confidentiality of randomization, only the physician administering the study drug will know which group the subject(s) is/are in for both experimental and control group. All data and records generated during this study will be kept confidential in accordance with institutional policies and HIPAA on subject privacy. The study investigators will not use such data and records for any other purpose other than conducting the study. Privacy protection procedures are in place and good clinical practice guidelines will be followed throughout the study to minimize the risks associated with breach of confidentiality. This risk will be minimized by strict compliance with HIPAA procedures for securing PHI. Information that could be used to identify the subject will only be shared with researchers who have approval of the IRB.

The investigator and sponsor have the right to discontinue a subject from study treatment or withdraw a subject from the study at any time. If a subject is discontinued from the study at the discretion of a PI or other delegated individual, the reason for discontinuation procedures will be noted in the subject's research record.

An investigator may terminate participation in the study if, but are not limited to:

Subject withdrawal of consent at any time

May 2, 2022 Version: 1.23

Page 13

- Disease progression
- Intolerable toxicity
- Any medical condition that the investigator or sponsor determines may jeopardize the subject's safety if the subject continues treatment with the study drug
- The investigator or sponsor determines it is in the best interest of the subject
- Failure of the subject to adhere to protocol procedure requirements
- Study termination by sponsor

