10.2 Analysis Datasets

The study dataset consists of 30 subjects; 15 of whom will be randomized to receive a sub anesthetic single bolus of ketamine (0.6 mg/kg) following robotic removal of endometriosis and 15 of whom will be randomized to receive an equal volume saline bolus as control. All analyses will be treated as intention to treat based on the randomization of study subjects to either the ketamine arm or placebo arm.

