13.5 Participant and Data Confidentiality

Information about study subjects will be kept confidential and managed according to the requirements of the Health Insurance Portability and Accountability Act of 1996 (HIPAA). Those regulations require a signed subject authorization informing the subject of the following:

- What protected health information (PHI) will be collected from subjects in this study
- Who will have access to that information and why
- Who will use or disclose that information
- The rights of a research subject to revoke their authorization for use of their PHI.

In the event that a subject revokes authorization to collect or use PHI, the investigator, by regulation, retains the ability to use all information collected prior to the revocation of subject authorization. For subjects that have revoked authorization to collect or use PHI, attempts should be made to obtain permission to collect at least vital status (i.e., that the subject is alive) at the end of their scheduled study period.

Participant confidentiality is strictly held in trust by the participating investigators, their staff, and the sponsor(s) and their agents. Therefore, the study protocol, documentation, data, and all other information generated will be held in strict confidence. No information concerning the study or the data will be released to any unauthorized third party without prior written approval of the sponsor.

The study monitor, other authorized representatives of the sponsor, representatives of the IRB or pharmaceutical company supplying study product may inspect all documents and records required to be maintained by the investigator, including but not limited to, medical records (office, clinic, or hospital) and pharmacy records for the participants in this study. The clinical study site will permit access to such records.

May 2, 2022 Version: 1.23

2, 2022 Page 29

The study participant's contact information will be securely stored at each clinical site for internal use during the study. At the end of the study, all records will continue to be kept in a secure location for as long a period as dictated by local IRB and Institutional regulations.

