14.2 Study Records Retention

Study documents will be retained for the longer of 3 years after close-out, 5 years after final reporting/publication. No records will be destroyed without the written consent of the sponsor, if applicable. It is the responsibility of the sponsor to inform the investigator when these documents no longer need to be retained.

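### Section 5.7.2 has data discarded after withdrawal of consent and leaves retention of earlier data open, in conflict with 2.4.2, 5.7.1, 13.5, 14.2 and the intention-to-treat analysis in 10.2

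*Combined protocol and SAP*

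**What the plan says.** Section 5.7.2 covers enrolled participants who withdraw consent, verbally or in writing. Four of its statements matter here:

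- On disposal: "Any data remaining after formal withdrawal, will be destroyed/discarded per Institutional guidelines".
- On earlier data: "Subject will be informed whether the data will be retained and analyzed up to the point of withdrawal".
- On safety: the team is to make every effort to continue protocol safety follow-up and capture adverse events, serious adverse events and unanticipated problems.
- On numbers: "If subjects withdraw or discontinue early replacement participants will be allowed".

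Other sections treat the same data differently:

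- Section 5.7.1, with nearly the same text in 2.4.2 (Protection against Risks), says participants are told that "their withdrawal only affects uses and sharing of information after their written request to withdraw authorization has been received". It adds that authorization cannot be withdrawn for uses already made or needed to complete analyses or report data.
- Section 13.5 says that after revocation the investigator "retains the ability to use all information collected prior to the revocation of subject authorization".
- Section 14.2 keeps study documents for the longer of 3 years after close-out or 5 years after final reporting, and adds: "No records will be destroyed without the written consent of the sponsor, if applicable".
- Section 10.2 says: "All analyses will be treated as intention to treat based on the randomization of study subjects".

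**The concern.** A coordinator handling a withdrawal would turn to 5.7.2. That section has data discarded, and nothing in it says that values recorded before withdrawal are exempt. Deletion cannot be reversed.

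The exposed data are those already in hand: baseline scores, the POD 0 side-effect questionnaire, POD 0 and POD 1 opioid use, and POD 1 VAS, EHP-30, GAD-7 and MADRS. The repeated-measures model in 10.3.2 can use a participant who contributes baseline and POD 1 only, but not one whose record has been erased.

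Replacement adds to this. If a withdrawn participant is erased and another is randomized in her place, the dataset can still show the 30 subjects described in 10.2 while omitting someone who was randomized and dosed. The analysis would be labelled intention to treat but would have moved towards completers. Section 10.3.5 would report how many left and why, but it would not recover their values, and section 10 plans no missing-data sensitivity analysis.

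**Working it through.** The point is mainly textual, so the passages are tested on one case. Suppose a participant is randomized and dosed on POD 0, completes POD 1, and withdraws consent by telephone at POD 27.

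1. **5.7.2, disposal sentence.** Verbal notice is enough. If remaining data means whatever the study holds at that moment, her POD 0 and POD 1 records are discarded, subject to institutional guidelines that the protocol does not set out.
2. **5.7.2, next sentence.** She is told whether those records are kept. The section does not say what she is told.
3. **2.4.2 and 5.7.1.** Withdrawal of authorization acts only forward and only from a written request. Her earlier records stay usable, including for completing analyses.
4. **13.5.** Even after revocation, earlier information remains usable.
5. **14.2.** Records are kept for years, and destruction needs the sponsor's written consent where that applies.
6. **10.2 and 10.3.2.** She belongs to her randomized arm, and her POD 1 score enters the model.

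Steps 3 to 6 keep her data; step 1 on this reading does not, and step 2 does not decide.

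**Alternative reading.** Suppose remaining data means only data arising after withdrawal. The conflict with 2.4.2, 5.7.1 and 13.5 then largely disappears. But 5.7.2 also asks for adverse events to be captured after withdrawal, so the same paragraph would collect records and discard them. Neither reading makes the section consistent.

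**Could the sentence concern only people who never joined?** No. Section 5.4 separately has information from ineligible or declining patients destroyed, and 5.7.2 deals with subjects who withdraw consent.

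**Size.** One participant is 1/15 = 6.7% of an arm.

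The plan's own power figure is a useful check. Section 10.4 gives 80% power for 15 per arm, effect size 1.1, two-sided alpha 0.05, Wilcoxon rank-sum test, normal data. Simulation with 40,000 runs gives 79.6% (exact test) to 80.9% (asymptotic, no continuity correction), so the figure reproduces and is not at fault.

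The documents give no rate of consent withdrawal after randomization. As an assumption only, let 0 to 5 participants per arm be erased and not replaced. For one between-arm comparison at effect size 1.1, exact to asymptotic:

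| Left per arm | Power |
|---|---|
| 15 | 80–81% |
| 13 | 73–75% |
| 12 | 69–71% |
| 10 | 59–63% |

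This applies to visits where data had already been collected, chiefly POD 1. Retention does not create POD 83 values for someone who left at POD 27. Replacement can restore the count, but not the randomized set.

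**The case against.** The strongest reply is that this is loose drafting rather than an order to delete. The phrase about remaining data is undefined and limited by institutional guidelines. The following sentence contemplates retention and analysis up to withdrawal. Read with 2.4.2, 5.7.1 and 13.5, a careful team would keep the data. This stands in part: loss is possible, not certain. It does not settle the matter, because the section that governs withdrawal never says the data are kept.

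Further points that stand:

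- Adverse-event capture is required separately in 5.7.2, 8.3 and 8.4.1, and opioid use and drug administration are also in the medical record. This lowers the risk to safety data. A duty to record is not a rule on what is kept after withdrawal, however.
- Section 13.5 gives an ability to use data, not a duty to keep them, and the consent clause in 14.2 applies only where applicable.
- Stopping study drug is a different event. Under 5.7.1 such participants continue visits with consent, and 7.2.5 has participants told that they may stop the drug and stay in the study. Only full withdrawal of consent is affected.
- Verbal withdrawal of consent in 5.7.2 and written withdrawal of authorization in 2.4.2 and 5.7.1 can be two acts with two effects, so the difference in form is not in itself a contradiction.

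A reader might infer that retention is decided participant by participant once outcomes are known. The text says only that the subject is informed; one study-wide policy fits equally well.

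**Conclusion.** The inconsistency is real and should be corrected. Read plainly, 5.7.2 allows irreversible loss of data already collected from a randomized participant who withdraws consent. Combined with replacement, that would move the analysed set away from intention to treat. The conclusion rests on the plain reading of the disposal sentence and on the absence of any rule in 5.7.2 that exempts earlier data.

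Beyond 6.7% of an arm per erased participant, the size cannot be stated, and the power range shown is conditional on an assumed loss. Three stronger inferences are tempting but not supported:

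- **That deletion favours ketamine on pain.** Nothing in the documents links an unpleasant psychological reaction to a higher POD 1 VAS. The direction of any bias is unknown.
- **That the 12 percent emergence-reaction figure in 2.4.1 sizes the hidden harm.** It is general risk text, not tied to this dose or setting, and using it would presume that affected participants withdraw consent and are erased.
- **That enrolling about 50 to maintain 30 (5.6) gives the rate of loss.** That count starts at enrollment. Consent may precede surgery by up to two months (section 5) and randomization is on the day of surgery (4.1), so an unknown part of the loss comes before randomization, when there are no postoperative data to lose.

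**What to change.** 1. In 5.7.2, replace the disposal sentence with wording such as: *All data collected up to the date of withdrawal, including adverse events, are retained and included in the intention-to-treat and safety analyses. No new data are collected after that date except as the participant permits.*
2. In the next sentence, change *whether* to *that*, so the subject is told that data up to withdrawal are retained and analysed.
3. State how verbal withdrawal of consent (5.7.2) relates to written withdrawal of authorization (2.4.2 Protection against Risks, 5.7.1), and what each does to the data. Keep them as separate acts.
4. Check that the consent form says the same. It is a separate attachment and was not available for this review, so it may already agree.

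The cost is protocol wording, and consent wording if needed, through an IRB modification. No visit, assessment or analysis is added.

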5.8 Premature Termination or Suspension of Study

This study may be temporarily suspended or prematurely terminated if there is sufficient reasonable cause. If the study is prematurely terminated or suspended, the PI will promptly inform the IRB and will provide the reason(s) for the termination or suspension.

Circumstances that may warrant termination or suspension include, but are not limited to:

- Determination of unexpected, significant, or unacceptable risk to participants.
- Demonstration of efficacy that would warrant stopping.
- Insufficient compliance to protocol requirements.
- Data that are not sufficiently complete and/or evaluable.
- Determination of futility.

May 2, 2022 Version: 1.23 Page 14

Study may resume once concerns about safety, protocol compliance, and/or data quality are addressed and satisfy the sponsor, IRB.

6 Study Agent (Study drug, device, biologic, vaccine etc.) and/or Procedural Intervention

Ketamine is an FDA-approved general anesthetic and analgesic agent that has been safely used clinically over the last 50 years. For general anesthesia, the intravenous induction doses range from 1 mg/kg to 4.5mg/kg. At subanesthetic doses (<1mg/km), ketamine is a potent analgesic with a clinically effective half-life of 45 min. 6,43,44 Off label it is also used as a powerful antidepressant and anxiolytic as a single dose (0.3-0.6 mg/kg) which can produce up to 14 days of mood stabilization. 8-10,45

This study is IND exempt as 21 CFR 312.2(b)(1) and 21 CFR 312.2(b)(5) as the study meets all the following criteria:

- 1. The drug product is lawfully marketed in the US.
- 2. The investigation is not intended to be reported to FDA as a well-controlled study in support of new indication and there is no intent to use it to support any significant change in the labeling of the drug.
- 3. In the case of a prescription drug, the investigation is not intended to support a significant change in the advertising for the drug.
- 4. The investigation does not involve a route of administration, dose, patient population, or other factor that significantly increase the risk (or decreases the acceptability of the risk) associated with the use of the drug product.
 - a. The risks for ketamine are well studied. In general, ketamine is a well-tolerated medication. 1,6,14,20 In previous studies for depression and pain, a dose range of 0.3-0.6 mg/kg was used. In a prior NYU study of ketamine for bariatric surgery, we used 0.4 mg/kg for ideal body weight.31 To further evaluate a single dose of ketamine for postoperative pain, we will use 0.6 mg/kg, which is in the range of the therapeutic dose for mood disorders and pain. 1,2,7,12,14,15,20,21
- 5. The investigation is conducted in compliance with the requirements for review by an IRB and with the requirements for informed consent.
- 6. The investigation is conducted in compliance with 21 CFR 312.7 (no intention to promote or commercialize the drug product).
- 7. The clinical investigation involves a placebo **and** the investigation does not otherwise require submission of an IND (refer to the sections above).

6.1 Study Agent(s) and Control Description

Ketamine [(+/-)-2-(2-chlorophenyl)-2-(methylamino)-cyclohexanone] is a white, crystalline powder or clear liquid. It is a schedule III substance and is classified as a dissociative anesthetic. Ketamine is available as a racemic mixture with the S- (+)- isomer being more potent than the R- (-)- isomer. It is commercially supplied as the hydrochloride salt in 0.5 mg/mL and 5 mg/mL ketamine base equivalents. Clinically, it is commonly used as an anesthetic induction agent for diagnostic and surgical procedures prior to the administration of general anesthetics. It is also used as a low dose infusion for analgesia.

Ketamine is an FDA-approved general anesthetic and analgesic agent that has been safely used clinically over the last 50 years. For general anesthesia, the induction dose ranges from 1mg/kg to 4.5 mg/kg. At sub anesthetic doses (< 1mg/kg), ketamine is a potent analgesic with a clinically effective half-life of 45 min. It is also a powerful antidepressant and anxiolytic, as a single dose (0.3-0.6 mg/kg) which can produce up to 14 days of mood stabilization.

Saline is a prescription medicine used for fluid and electrolyte replenishment for intravenous administration. 0.9% normal saline will be used as the placebo in the control group.

Version: 1.23

Page 15 May 2, 2022

6.1.1 Acquisition

Ketamine or saline will be ordered and obtained from NYULH inpatient pharmacy.

6.1.2 Formulation, Appearance, Packaging, and Labeling

Ketamine is a nonbarbiturate general anesthetic chemically designated dl 2-(0-chlorophenyl)-2(methylamino) cyclohexanone hydrochloride. It is formulated as a slightly acidic (pH 3.5-5.5) sterile solution for intravenous or intramuscular injection. Ketamine is available from NYULH inpatient pharmacy in concentrations of 50 mg/ml.

Saline is a prescription medicine used for fluid and electrolyte replenishment for intravenous administration. It will serve as the placebo drug in this study.

6.1.3 Product Storage and Stability

The study drug should be stored between 20° to 25°C (68° to 77°F).

The control solution, 0.9% normal saline will be stored at temperatures between 20° 25°C (68° to 77°F).

6.1.4 Preparation

The study drug will be obtained from NYULH inpatient pharmacy [contact]). The study physician is not blinded. Ketamine will be diluted to 10 mg/ml in normal saline by study physician. 0.9% normal saline will be used as the control.

6.1.5 Dosing and Administration

Single bolus ketamine: For the single bolus dose arm, ketamine at a dose of 0.6 mg/kg will be administered while the participant is recovering in the PACU on the day of surgery. The study drug will be administered over at least 30 minutes at one time point and will be administered after subject has been deemed to be stable (hemodynamically stable, awake) by the study team on POD 0.

Control/Placebo: Participants randomized into this group will receive matching volume of saline infusion in the PACU over at least 30 minutes at one time point (no ketamine).

6.1.6 Route of Administration

The planned route of administration is intravenous for the ketamine study drug and placebo drug.

6.1.7 Duration of Therapy

Approximately 30 Minutes.

6.1.8 Tracking of Dose

Drug protocol adherence will be recorded and verified through patient's electronic medical record and REDCap.

6.2 Study Agent Accountability Procedures

Study drug will be ordered by study physician when participant arrives to PACU. Regular study drug reconciliation will be performed to document drug assigned, drug consumed, and drug remaining. This reconciliation will be logged on the drug reconciliation form, signed, and dated by the study team. Unused study drug will be wasted with witness.

Version: 1.23

May 2, 2022 Page 16

Study Procedures and Schedule

Study Procedures/Evaluations 7.1

7.1.1 Study Specific Procedures

- Assessment of eligibility should include a review of permitted and prohibited medications.
- Assessment of study agent adherence
- Assessment of current and former Opioid Use
- Assessment of Side Effects/Adverse Events
- Administration of Visual Analogue Scale for pelvic pain assessment
- Administration of questionnaire packet including: EHP-30, GAD-7, and MADRS

7.1.2 Standard of Care Study Procedures

- Medical history
- Medication history

7.2 Study Schedule

7.2.1 Screening

Screening/Introductory Visit (Day -28 to -1)

- Introduce study and discuss participation
- Obtain medical history and medications history
- Review and verify inclusion/exclusion criteria
- Refer eligible participants to research coordinator
- Schedule baseline visit for participants who have been screened for eligibility and interested in participating and/or learning more about the study

7.2.2 Enrollment/Baseline

Enrollment/Baseline Visit (Visit 1, Day 0)

- Review and verify inclusion/exclusion criteria
- Obtain informed consent of potential participant verified by signature on written informed consent or electronic consent
- Obtain demographics information
- Complete baseline/enrollment survey
- Identify and document endometriosis staging
- Identify and document final procedure(s) list
- Review and verify medical history, medication history, and demographic information
- VAS assessment of pelvic pain
- Subjects will complete the questionnaire packet for assessments which will include, EHP-30, GAD-7, DN-4, and MADRS guestionnaires. Opioid use and adverse events will also be assessed via subject reporting and medical record review. This will be done either in person, over the phone, or electronically via REDCap link sent to subject

